12 PLANNED STATISTICAL METHODS

12.1 General Considerations

This section describes the statistical analysis as foreseen at the time of planning the study. Changes, additions, and further details about the analyses will be described in the statistical analysis plan (SAP). After finalization of the SAP, any additional analyses or changes to analyses that may be required will be fully disclosed in the Clinical Study Report (CSR.).

Analyses will be performed after the database lock at which all eCRFs are completed, entered and source data verified; all safety laboratory results have been reported; all AEs fully characterized (e.g., relationship to test article determined) and coded; characterization of protocol deviations as major/minor completed, and all queries have been resolved.

Exploratory analyses may also be performed. Listings of individual subject's data will be produced.

12.2 Determination of Sample Size

This study is designed to evaluate the PK profile of an oral dosing regimen, 300mg BID on Day 1 and QD on Day 2, in adults with CABP. The sample size determination is based on consideration of the precision of the estimate, GMR of AUC₍₀₋₄₈₎ for 300mg po to 100mg IV, derived from model-based simulations of omadacycline concentration data (Phase I studies).

With 20 evaluable subjects, there will be 90% probability that the 90% CIs of the GMR for $AUC_{(0-48)}$ will be within 80% and 125%. Up to 30 subjects will be enrolled so that at least 20 subjects are evaluable for bioavailability estimation.

The number may be adjusted as needed to meet this requirement.

12.3 Analysis Populations

The following subject analysis populations have been defined for the various analyses of PK, safety and efficacy:

- The PK population will consist of all assigned subjects who receive test article and have PK samples collected.
- The Safety population will consist of all assigned subjects who receive at least one dose of test article.
- The intent-to-treat (ITT) population will consist of all assigned subjects.

Additional populations may be defined in the SAP as appropriate.

12.4 Demographics and Baseline Characteristics

Demographics (including age, ethnicity and race) and baseline characteristics will be summarized. Descriptive statistics of the duration of test article treatment will be provided. The number and percentage of subjects who prematurely discontinued test article and the reason for discontinuation and the number and percentage of subjects prematurely discontinuing the study and the primary reason for discontinuation will be presented.

12.5 Primary Endpoint(s)

12.5.1 Pharmacokinetic Endpoint

The following plasma PK parameters will be determined:

- Area under the plasma concentration time curve (AUC) from time 0 to 48 hours after dosing (AUC₀₋₄₈)
- Area under the plasma concentration time curve (AUC) from time 0 to 24 hours after dosing (AUC₀₋₂₄)
- AUC from time 0 to the last quantifiable concentration (AUC_{last})
- Maximum observed plasma concentration (C_{max})
- Time to reach maximum observed plasma concentration (T_{max})
- Elimination half-life associated with the terminal slope of the semilogarithmic concentration-time curve $(T_{1/2})$

The observed omadacycline concentration-time data after an oral dosing regimen, BID on Day 1 and QD on Day 2, in CABP patients will be evaluated. 300mg administered orally is the dose that provided equivalent total exposure as measured by AUC relative to the 100mg IV dose (CPTK796-A2104). The oral bioavailability of omadacycline is 34%.

Using the superposition principle, the AUC of a single 100mg IV dose on Day 1 for n=63 healthy subjects were totaled to evaluate the AUC₍₀₋₄₈₎ of the established omadacycline IV dosing regimen (q12h on Day 1 followed by q24h on Day 2). AUC₍₀₋₄₈₎ values are then summarized and serve as the comparator for this current study. Safety and efficacy in CABP patients were demonstrated with this dosing regimen (PTK796-CABP-1200), but only sparse PK sampling was conducted. The final population PK model for omadacycline, which includes CABP patients from the PTK0796-CABP-1200 study, generated similar AUC₍₀₋₄₈₎ values for the 100mg IV dosing regimen.

The comparative bioavailability assessment between the test, 300mg po in CABP patients, and the reference, 100mg IV in healthy subjects, will be based on 90% confidence intervals (CIs) for the geometric mean ratios (GMR) of AUC₍₀₋₄₈₎ for the two dosing regimens being within 80% and 125%.

Plasma concentration data and PK parameters will be summarized by time point using descriptive statistics (number of subjects, mean, standard deviation (SD), coefficient of

variation (CV), median, minimum, and maximum). Mean and individual plasma concentration versus time profiles will be presented in figures on both linear and semilogarithmic scales. Geometric means will be included for area under the concentration-time curve (AUC) and maximum observed plasma concentration (C_{max}).

Individual plasma concentration, time deviation and PK parameters will be presented in data listings.

Any additional exploratory PK calculations will be further described in the SAP.

12.6 Secondary Endpoint(s)

12.6.1 Safety Endpoint(s)

All safety analyses will utilize the Safety population. Summary tables will be provided for all treatment-emergent adverse events (TEAEs). A TEAE is defined as an AE with a start date and time on or after the first dose of test article. Adverse events will be coded using the Medical Dictionary for Regulatory Activities (MedDRA) and will be summarized by presenting the number and percentage of subjects having each TEAE by system organ class (SOC) and preferred term (PT), by SOC, PT and severity, and by SOC, PT and relationship to test article. Additional tabulations will provide summarise by SOC and PT of subjects experiencing SAEs and TEAEs leading to discontinuation of test article. Treatment-emergent adverse events leading to dose interruption of test article, and TEAEs of special interest.

The following variables will be analyzed descriptively in the Safety population:

- Vital signs (systolic and diastolic BP, pulse/heart rate, body temperature, pulse oximetry, RR), including change from Baseline by time point measured
- Clinically notable vital signs (meeting predefined criteria as specified in the SAP) by time point measured
- Laboratory parameters, including change from Baseline by visit and overall worst post-baseline
- Clinically notable laboratory parameters (meeting predefined criteria as specified in the SAP) by visit and overall worst post-baseline

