- 1. Has received more than 24 hours (ie, a single dose of a daily therapy or the recommended daily frequency of a short acting therapy) of a potentially effective systemic antibacterial treatment within the 72 hours prior to the first dose of test article. A subject will be considered to have received a potentially effective systemic antibacterial treatment if the pathogen identified as causing infection is shown to be susceptible to the antibacterial given or, in the circumstance where a pathogen is not identified, if the antibacterial agent is approved for treatment of pneumonia or is known to have activity against any of the leading causes of CABP (eg, *Streptococcus pneumoniae, Haemophilus influenzae, Moraxella catarrhalis, S. aureus, Legionella pneumophila*).
- 2. Is known or suspected to have CABP caused by a pathogen that may be resistant to test article (eg, *Pseudomonas aeruginosa*, *Proteus* spp., *Morganella morganii*, *Providencia* spp., *Pneumocystis jiroveci*, obligate anaerobes, mycobacteria, fungal pathogens).
- 3. Suspected or confirmed empyema (a parapneumonic pleural effusion is not an exclusion criterion) or lung abscess.
- 4. Subjects who reside in a long-term care or subacute/intermediate healthcare facility (eg, nursing home) or a subject diagnosed with pneumonia following a recent hospitalization (overnight admission within 90 days prior to current admission).
- 5. Has a known history of having experienced unstable cardiac disease (eg, unstable angina, myocardial infarction, acute congestive heart failure, unstable cardiac arrhythmia) within the 3 months prior to Screening or presents with a tachyarrhythmia (excluding sinus tachycardia).
- 6. Has any of the following at Screening:
 - alanine aminotransferase (ALT) or aspartate aminotransferase (AST) ≥ 3 × Upper Limit of Normal (ULN)
 - total bilirubin $> 1.5 \times ULN$
 - suspected or confirmed clinical evidence of end-stage liver disease (eg, ascites, hepatic encephalopathy)
- Requires any form of dialysis (eg, hemodialysis, peritoneal dialysis), has a history or evidence of severe renal disease, or has a calculated creatinine clearance (CrCl) of < 30 mL/minute, using the Cockcroft-Gault equation (see calculation in Appendix 2).
- 8. Significant immunological compromise determined by any of the following:

- Current or anticipated neutropenia defined as < 500 neutrophils/mm³

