8.3 Laboratory Values

Summaries of laboratory data will include hematology, and chemistry, parameters. Laboratory parameters will be presented in alphabetic order with the following exceptions: differentials of white blood cell (WBC) counts will be presented following the WBC results, and chemistry parameters will first be grouped by organ class (renal, liver, electrolytes, and other) and presented alphabetically within each of these classes, as shown below.

Organ Class	Laboratory Parameter
Renal	Creatinine
Renal	Urea
Liver	Alkaline phosphatase (ALP)
Liver	ALT
Liver	AST
Liver	Total Bilirubin
Liver	GGT
Electrolytes	Bicarbonate
Electrolytes	Calcium
Electrolytes	Chloride
Electrolytes	Magnesium
Electrolytes	Potassium
Electrolytes	Sodium
Other	Albumin
Other	Amylase
Other	Blood glucose
Other	Cholesterol
Other	CK
Other	LDH

Table 1.Laboratory Parameters and Organ Class

Organ Class	Laboratory Parameter
Other	Lipase
Other	Phosphate
Other	Total protein
Other	Uric acid

Table 1.Laboratory Parameters and Organ Class

Baseline is defined the local lab value that is closest to and prior to the first dose of study drug.

Several analyses of the laboratory data will be presented. Descriptive statistics (based on International System [SI] units) for chemistry, hematology and the change from baseline will be summarized by treatment group at each time point (EOT Visit and PTE Visit), and for the overall worst value post-baseline (which includes unscheduled visits).

Clinically notable laboratory values will be defined as any lab values with at least a 2-grade increase from baseline. Shift tables will be presented to show the number of subjects with a laboratory value with a grade of 0, 1, 2, 3 or 4 at baseline versus the value at each visit and the worst post-baseline value. Number and percentage of subjects with at least a 2-grade increase from baseline (based on DMID criteria shown in Appendix 3) will be summarized. Percentages for each laboratory test will be based on the number of subjects with a baseline and post-baseline evaluation of the specific laboratory test. A listing will be provided which gives all laboratory results for a given laboratory test for subjects who have at least one 2-grade increase from baseline.

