10.4 Clinically Notable Values

- Clinically notable laboratory parameters, meeting predefined criteria as values with 2 grade increases will be listed
- Clinically notable vital signs, meeting predefined criteria as specified in Appendix 4 by time point measured

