Appendix 3 Modified Division of Microbiology and Infectious Diseases Adult Toxicity Table

The DMID Adult Toxicity Table (21-NOV-2007) was modified to exclude the clinical component of the toxicity grading because clinical signs and symptoms related to abnormal laboratory values are not collected in this study. In addition, Grade 0 was added to the table so that shifts from normal could be analyzed. Grades for enzymes were modified as indicated in the table below.

For toxicity grades based on a multiple of the ULN, the normal range from the central laboratory will be applied.

For toxicity grades based on fixed values, the grades will be assigned regardless of the normal actual range values from the central laboratory. For example, a hemoglobin value of 10.0 gm/dL will be assigned a grade of 1 toxicity, even if the lower limit of normal from the laboratory was 9.8 gm/dL.

HEMATOLOGY									
	Grade 0	Grade 1	Grade 2	Grade 3	Grade 4				
Hemoglobin (gm/dL)	> 10.5	9.5-10.5	8.0-9.4	6.5-7.9	< 6.5				
Absolute Neutrophil Count (count/mm ³)	> 1500	1000-1500	750-999	500-749	< 500				
Platelets (count/mm ³)	\geq 100,000	75,000-99,999	50,000-74,999	20,000-49,999	< 20,000				
WBCs (count/mm ³)	1000-10,999	11,000-12,999	13,000-14,999	15,000-30,000	> 30,000 or < 1,000				

		CHEMISTRY	Y		
	Grade 0	Grade 1	Grade 2	Grade 3	Grade 4
Hyponatremia (mEq/L)	> 135	130-135	123-129	116-122	< 116
Hypernatremia (mEq/L)	< 146	146-150	151-157	158-165	> 165
Hypokalemia (mEq/L)	> 3.4	3.0-3.4	2.5-2.9	2.0-2.4	< 2.0
Hyperkalemia (mEq/L)	< 5.6	5.6-6.0	6.1-6.5	6.6-7.0	> 7.0
Hypoglycemia (mg/dL)	≥ 65	55-64	40-54	30-39	< 30
Hyperglycemia (mg/dL) (nonfasting and regardless of prior history of diabetes)*	< 116	116-160	161-250	251-500	> 500
Hypocalcemia (mg/dL) (corrected for albumin)	> 8.4	8.4-7.8	7.7-7.0	6.9-6.1	< 6.1
Hypercalcemia (mg/dL) (correct for albumin)	≤ 10.5	10.6-11.5	11.6-12.5	12.6-13.5	> 13.5
Hypomagnesemia (mEq/L)	> 1.4	1.4-1.2	1.1-0.9	0.8-0.6	< 0.6
Hypophosphatemia (mg/dL)	≥ 2.5	2.0-2.4	1.5-1.9	1.0-1.4	< 1.0
Hyperbilirubinemia (total bilirubin)	< 1.1×ULN	1.1-1.5×ULN	> 1.5- 2.5×ULN	> 2.5-5×ULN	> 5×ULN
Urea	< 1.25×ULN	1.25-2.5×ULN	> 2.5-5×ULN	> 5-10×ULN	$> 10 \times ULN$
Hyperuricemia (uric acid) (mg/dL)	< 7.5	7.5–10.0	10.1–12.0	12.1–15.0	> 15.0
Creatinine	< 1.1×ULN	1.1-1.5×ULN	> 1.5- 3.0×ULN	> 3.0-6×ULN	>6×ULN

*The DMID toxicity table reports hyperglycemia detected in nonfasting specimens obtained from subjects with no prior diabetes.

ENZYMES										

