	Grade 0	Grade 1	Grade 2	Grade 3	Grade 4					
AST (SGOT)	< 1.25×ULN	1.25-2.5×ULN	> 2.5-5×ULN	> 5-10×ULN	>10×ULN					
ALT (SGPT)	< 1.25×ULN	1.25-2.5×ULN	> 2.5-5×ULN	> 5-10×ULN	>10×ULN					
GGT	< 1.25×ULN	1.25-2.5×ULN	> 2.5-5×ULN	> 5-10×ULN	>10×ULN					
Alkaline	< 1.25×ULN	1.25-2.5×ULN	> 2.5-5×ULN	> 5-10×ULN	>10×ULN					
Phosphatase										
Amylase	< 1.1×ULN	1.1-1.5×ULN	> 1.5-2.0×ULN	> 2.0-5.0×ULN	> 5.0×ULN					
Lipase	< 1.1×ULN	1.1-1.5×ULN	> 1.5-2.0×ULN	> 2.0-5.0×ULN	> 5.0×ULN					

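### The clinically notable laboratory rule (a rise of at least 2 grades) never counts a worsening from Grade 2 to 3 or Grade 3 to 4, and its denominator keeps subjects whom it cannot flag

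*Protocol*

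**What the plan says.** Protocol 12.6.1 makes this a safety variable and defers the definition: "Clinically notable laboratory parameters (meeting predefined criteria as specified in the SAP) by visit and overall worst post-baseline". SAP 8.3 defines it: "Clinically notable laboratory values will be defined as any lab values with at least a 2-grade increase from baseline". SAP 10.4 restates the rule: "Clinically notable laboratory parameters, meeting predefined criteria as values with 2 grade increases will be listed". Neither section gives a second trigger, such as reaching a given grade.

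Within SAP 8.3 the same rule produces three outputs: the number and percentage of subjects, the CN flag in the subject listings (last paragraph of the section), and a focused listing of all results for a test in subjects who meet the rule on it. On the denominator, SAP 8.3 says: "Percentages for each laboratory test will be based on the number of subjects with a baseline and post-baseline evaluation of the specific laboratory test".

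The grades come from the modified toxicity table in SAP Appendix 3, which runs from 0 to 4.

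**The concern.** A rule based only on grade change loses sensitivity as the baseline grade rises. A subject normal at entry is flagged on reaching Grade 2. A subject who enters at Grade 2 is flagged only at Grade 4, and one who enters at Grade 3 or 4 cannot be flagged on that scale at all. The rule can therefore call a small, mild change notable and pass over a larger one that ends at a more severe grade.

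This bears on the trial for two reasons. Safety is the secondary objective, and the notable count is the programmed summary of laboratory safety. Entry also admits abnormal values: a WBC count above 12,000 cells/mm³ is one of the findings that satisfies inclusion criterion 5 (Protocol 6.2), and ALT or AST is excluded only from 3 × ULN upward (exclusion criterion 6).

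The SAP handles vital signs differently. Under SAP 8.2 and Appendix 4 an absolute criterion value is always part of the definition. The laboratory rule has no absolute component.

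**Working it through.** The plan states no figure to reproduce, so the check applies the rule to the SAP's own grade table.

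**Inputs**
- Rule (SAP 8.3, 10.4): flag if post-baseline grade − baseline grade ≥ 2.
- ALT, Grades 0 to 4 (SAP Appendix 3): "ALT (SGPT) < 1.25×ULN 1.25-2.5×ULN > 2.5-5×ULN > 5-10×ULN >10×ULN".
- WBC per mm³, Grades 0 to 4 (SAP Appendix 3): "1000-10,999 11,000-12,999 13,000-14,999 15,000-30,000 > 30,000 or < 1,000".
- Hemoglobin in g/dL (SAP Appendix 3): Grade 0 above 10.5; Grade 1, 9.5–10.5; Grade 2, 8.0–9.4; Grade 3, 6.5–7.9; Grade 4 below 6.5.

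**Step 1: all grade pairs.** A 0 to 4 scale has 4 + 3 + 2 + 1 = 10 possible worsenings.
- Flagged (6): 0→2, 0→3, 0→4, 1→3, 1→4, 2→4.
- Not flagged (4): 0→1, 1→2, 2→3, 3→4. The last two end at Grade 3 or 4.

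Grades that trigger the flag, by baseline grade: from 0, Grades 2 to 4; from 1, Grades 3 and 4; from 2, Grade 4 only; from 3 or 4, none.

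**Step 2: illustrative values.**

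| Test | Change | Grades | Size | Notable? |
|---|---|---|---|---|
| Hemoglobin, g/dL | 10.6 → 9.4 | 0 → 2 | −1.2 | yes |
| Hemoglobin, g/dL | 9.4 → 6.5 | 2 → 3 | −2.9 | no |
| ALT, × ULN | 1.2 → 2.6 | 0 → 2 | 2.6/1.2 = 2.2-fold | yes |
| ALT, × ULN | 2.6 → 9.9 | 2 → 3 | 9.9/2.6 = 3.8-fold | no |
| WBC, per mm³ | 10,900 → 13,000 | 0 → 2 | +2,100 | yes |
| WBC, per mm³ | 16,000 → 45,000 | 3 → 4 | +29,000 | no |

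**Step 3: can such baselines enter the trial?**
- ALT of 2.6 × ULN is Grade 2 and below the 3 × ULN exclusion, so it can. From there nothing is flagged until ALT exceeds 10 × ULN.
- A WBC count above 12,000 is at least Grade 1, and from 15,000 it is Grade 3. A subject who qualifies on WBC at 15,000 or more therefore cannot be flagged on WBC.
- ALT and AST Grade 3 starts above 5 × ULN, and total bilirubin Grade 2 starts above 1.5 × ULN. Exclusion criterion 6 bars ALT or AST from 3 × ULN and bilirubin above 1.5 × ULN, so no eligible subject starts at Grade 3 or 4 on these three tests.

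**Step 4: weight of one subject.** With 30 subjects evaluated on a test, one uncounted subject changes the incidence by 1/30 = 3.3 percentage points; with 20, by 1/20 = 5.0 points.

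**Step 5: the rule with a Grade 3/4 condition added.** Pairs 2→3 and 3→4 become notable, so 8 of 10 worsenings count. Those left out, 0→1 and 1→2, end at Grade 1 or 2. Only baseline Grade 4 then remains impossible to flag.

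**The case against.** The SAP states one prespecified rule consistently, and Protocol 12.6.1 leaves the choice to it, so nothing is contradicted. Any cut on an ordinal scale will catch some small changes and miss some large ones. That is fair: this is a weakness in the choice of criterion, not an inconsistency.

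The second objection carries more weight. A reader might infer that these worsenings vanish from the report. They do not. SAP 8.3 says: "Shift tables will be presented to show the number of subjects with a laboratory value with a grade of 0, 1, 2, 3 or 4". These tables set the baseline grade against each visit and the worst post-baseline value, so every 2→3 and 3→4 shift is tabulated. Change from baseline is summarized by visit and for the worst value. All laboratory data are listed with low and high flags. Protocol 8.18.4 also allows a clinically significant abnormality to be recorded as an adverse event, though only on judgment. In an open-label study of up to 30 subjects with two scheduled post-baseline laboratory visits and no formal comparisons, these outputs can be read subject by subject.

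Three further inferences go too far:
- That an affected subject can never be flagged. The limit applies per test and per scale. Sodium, potassium, glucose and calcium have separate high and low scales, so a swing in the other direction could still be flagged.
- That many subjects are affected. The documents admit abnormal values but give no baseline grade distribution.
- That any ALT rise past 3 × ULN ought to be notable. That figure is an entry limit, and neither document uses it as a post-baseline safety threshold.

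**Conclusion.** The point holds in a limited form. On a given graded scale, worsenings from Grade 2 to 3 and from Grade 3 to 4 are never notable, and subjects at Grade 3 or 4 at baseline on that scale sit in the denominator without being able to reach the numerator. The effect is confined to the notable incidence, the CN flag and the focused listing.

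The grade-pair result follows from the rule alone. The laboratory values are illustrations and do not predict what subjects will show. The statement that ALT, AST and bilirubin cannot start at Grade 3 or 4 assumes that eligibility is respected and that the same ULN serves for eligibility and grading. The expected number of subjects affected cannot be estimated from the documents. The change is a worthwhile improvement to a descriptive safety summary; no study conclusion depends on it.

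**What to change.** In SAP 8.3, including the CN-flag wording in its last paragraph, and in SAP 10.4:
- Define a clinically notable laboratory value as at least a 2-grade increase from baseline, or any post-baseline Grade 3 or 4 value at least one grade above baseline.
- Base the percentage for each graded scale on subjects with baseline and post-baseline evaluations and a baseline below Grade 4.
- Show the count under the 2-grade rule alongside, for comparability with any study that used that rule alone.

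The cost is one added condition in the text and programming, using data already collected. The downside is a few more flagged subjects, some for small changes that cross a grade limit: glucose 250 to 251 mg/dL or WBC 14,999 to 15,000 (both Grade 2 to 3) would become notable. One-grade rises that end at Grade 1 or 2 would still not count.

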12.6.2 Exploratory Endpoint(s)

The efficacy outcome is defined as the Investigator's Assessment of Clinical Response with outcomes of Clinical Success, Clinical Failure or Indeterminate (see Section 8.12.1) in the ITT population.

An Indeterminate Response is included in the denominator for the calculation of the percentage of subjects with a Clinical Success in the ITT population and thus, is essentially considered a Clinical Failure.

The following is a list of key assessments that will be performed:

- Assessment of signs and symptoms of CABP by the investigator
- Clinical Stability

12.6.3 Resource Utilization Endpoint(s)

Data for resource utilization will be collected through the Final Follow-up assessment and will include:

- Hospital admission
- Emergency Department and Physician visits

Descriptive statistics for the resource utilization parameters will be provided for the purpose of health economic evaluation.

12.7 Data Handling Conventions

For all variables, only the observed data from the patients will be used in the statistical analyses, ie, there is no plan to estimate missing data, unless otherwise specified. Detailed data imputation rules will be described in the SAP.

If available, pharmacokinetic parameters from the concentration-time profile data of patients who drop out or are withdrawn will be calculated but will be excluded from the final statistical analysis.

